## **Objectives**

1. Adapt the Living Well in the Community peer led health promotion program to address the needs of families caring for adolescents living with a disability in rural, southeast Georgia.
2. Implement the adapted Living Well in the Community program in southeast Georgia.
3. Evaluate the adapted Living Well in the Community program.

Investigators will provide technical assistance to local Peer Facilitators and develop a Parent Facilitator Guide to accompany the Living Well in the Community program. A local community partner will recruit 20 families to participate in the pilot of the adapted program. Four members of the Navigator Team will serve as Parent Mentors and lead 5 families through adapted Living Well in the Community program. Investigators will 1) matching parent facilitators with families, 2) scheduling and confirming weekly meetings, 3) scheduling and confirming bi-weekly workshops and 4) leading bi-weekly workshops that will include extended programming for parents and children.

## **Hypothesis**

We hypothesize that families in participating in the program will experience increases in health-related quality of life, mental health, and physical activity.

## **Design**

Investigators will conduct a mixed-methods evaluation of the adapted curriculum including both children and youth participants to measure changes in outcomes and consumer satisfaction with the program.

## **Methods**

First, parent facilitators will be recruited and matched with their peers. Parent facilitators will be community members with a child with a disability. The peer matching resembles the community lay health worker model. The community lay health worker model will reduce the amount of time needed to meet face to face with families. To begin adapting the facilitator training and curriculum, the program directors will work with investigators to review and update training materials. Parent facilitators will undergo an online, intensive facilitator training. The facilitator training is approximately 15 hours long. The training includes three major components: peer training, facilitator training, and Master “Train the Trainer” training. Five parent facilitators will work together with investigators to deliver the adapted curriculum to participating families. With bi-weekly meetings for 10 weeks between parent facilitators and family participants in the home or another desired location. The investigators have already participated in the facilitator training and will serve as mentors to newly trained facilitators. At the end of the online training session, the parent facilitators will be equipped to successfully implement the Living Well curriculum. The investigators will schedule a working meeting before and after the facilitator training to discuss curriculum changes. Changes in readability are anticipated since the target audience includes adolescents. Curriculum delivery methods will need tailoring to match a family-based approach including activities to be completed at the home at the family and individual levels for parents, siblings, and children. Both investigators and parent facilitators will lead monthly summary meetings to review the adapted content. These meetings will take place at a convenient location in the community. Pre and post focus groups will take place before and after these monthly meetings at a convenient locale in the community.

## Instrumentation

**Quantitative.** The Patient Reported Outcomes Measurement Information System (PROMIS; see attached) will be used to examine mental health and physical activity. PROMIS has 4 unique features: comparability, reliability/validity, flexibility, and inclusiveness. Its measures have been standardized, allowing comparisons across subpopulations and with the general population. Recently, pediatric versions have been adapted for proxy reporting in the areas of mental, physical, and social health.

**Qualitative.** The project directors will conduct face to face interviews with the children living with disability participants and focus groups with the parent/caregiver participants to explore program effects and collect feedback on the adapted program. The project directors will aim to recruit 8-10 participants for the face-to-face interviews and 8-10 focus group participants from the families who participated in the curriculum. Both interviews and focus groups will last approximately 60 minutes. Interview and focus group guides will be developed and used to guide each interview and focus group. Interviews and focus groups will be recorded. Audio recordings will be transcribed verbatim. Transcripts will be analyzed using content analysis to identify codes and emergent themes.

The evaluation team will collect questionnaires pre and post implementation. Each facilitator will have an envelope to return to the evaluation team. The evaluation team will enter the data into a SPSS database and analyze the results. A Multivariate analysis of variance (MANOVA) will be conducted for each survey with appropriate post hoc tests. Interview and focus group guides will be developed and used to guide each interview and focus group. Interviews and focus groups will be recorded. Audio recordings will be transcribed verbatim. Transcripts will be analyzed using content analysis to identify codes and emergent themes.

Only data will only be presented in aggregate post analysis.

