## Statistical Analysis Overview

The evaluation team will collect questionnaires pre and post implementation. Each facilitator will have an envelope to return to the evaluation team. The evaluation team will enter the data into SAS database and analyze the results. We will evaluate differences between pre and post measures using a paired t-test for normally distributed data and Friedman's test for non-normally distributed scales.

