## Comments

A 5% increase in subscales are considered meaningful. With a 5% increase with a standard deviation of 0.1 and alpha = 0.007 (to account for multiple tests) power at N = 20 ranges from a low of 0.84 to a high of 0.99 calculated using SAS proc power.

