## **Statistical Test of Hypothesis**

Null: There is no differences in scale and subscale measures between pre and post outcome measures.

Alternative: There are differences in scale and subscale measures between pre and post outcome measures.

All data will be analyzed by paired t-tests/Friedman's test. To accommodate multiple comparisons, all p-values will be adjusted using Hochberg's adjustment.

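### Instrumentation plans a MANOVA for each survey with unnamed post hoc tests, while the statistical sections plan paired tests with one Hochberg adjustment; keep one rule and state how many tests lie behind alpha 0.007.

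*Combined protocol and SAP*

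**What the plan says.** The combined protocol and SAP describes the analysis of the pre and post questionnaires in two ways.

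- **Instrumentation:** "A Multivariate analysis of variance (MANOVA) will be conducted for each survey with appropriate post hoc tests". It does not name the post hoc method, the number of surveys, or any control of error across surveys.
- **Statistical Analysis Overview:** "We will evaluate differences between pre and post measures using a paired t-test for normally distributed data", with Friedman's test for scales that are not normally distributed. MANOVA is not mentioned.
- **Statistical Analyses and Statistical Test of Hypothesis:** both assign all data to paired t-tests or Friedman's test. Both add: "To accommodate multiple comparisons, all p-values will be adjusted using" Hochberg's method. The null hypothesis reads "There is no differences in scale and subscale measures between pre and post outcome measures", so scales and subscales are both tested. The Comments entry after P-Value repeats Hochberg, and P-Value sets .05.
- **Comments (power statement):** "A 5% increase in subscales are considered meaningful", and "alpha = 0.007 (to account for multiple tests) power at N = 20 ranges from a low of 0.84 to a high of 0.99". The number of tests is not given.

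Instrumentation and Statistical Analysis Overview give the same account of how the questionnaires are collected and returned. They then diverge: SPSS and MANOVA in one, SAS and paired tests in the other. They therefore concern the same data, and neither is marked as superseded.

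**The concern.** An analyst who follows Instrumentation and one who follows the statistical sections would run different procedures on the same data. The first opens a survey when its MANOVA is significant and then applies post hoc tests of the analyst's choosing. The second tests every scale and subscale and makes one Hochberg adjustment over all of them. The two can end with different lists of significant scales, and the choice could be made after the results are known.

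The post hoc method matters as much as the number of surveys. A significant MANOVA says only that something in the survey changed. Once one scale has truly changed, the gate tends to open, and unadjusted tests of the other scales in that survey are then unprotected. This can happen even if all scores belong to a single survey.

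The alpha in the power statement is tied to the same question. It is the strictest Hochberg step only for one particular number of tests, and the visible text does not give that number.

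**Working it through.** **1. The plan's alpha.** Hochberg's method compares the largest of m p-values with 0.05, the next with 0.05/2, and so on down to 0.05/m for the smallest. The strictest step is 0.05/6 = 0.0083, 0.05/7 = 0.0071 or 0.05/8 = 0.0063. Only m = 7 rounds to the stated 0.007. That seven tests were intended is an inference.

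**2. The plan's power.** For a two-sided paired t-test with N = 20, power = P(|T| > t(1 - alpha/2; 19 df)), where T is noncentral t with noncentrality d x sqrt(20), and d is the mean change divided by the SD of the change. Solving at alpha = 0.007 gives d = 0.914 for the stated 0.84 and d = 1.248 for the stated 0.99. These values are back-solved from the stated power. The plan does not say whether its SD of 0.1 is that of one measurement or of the change, and that separate question is not used here.

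**3. The two rules compared.** All settings here are assumptions: N = 20; seven normal change scores with common correlation 0.3 or 0.6; one survey of 7, two of 4 + 3, or three of 3 + 2 + 2; one score, in the largest survey, truly changed by d = 0.914. The pre/post MANOVA is taken as the paired Hotelling test: T2 = n x (mean change)' S^-1 (mean change), where S is the covariance matrix of the k change scores in the survey, and F = T2 (n - k) / [k (n - 1)] on k and n - k df, at 0.05 per survey. Each scenario had 30,000 or more simulated trials. Results are good to about one percentage point.

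| Rule | False positive on another score | List of significant scores differs from Hochberg over all |
|---|---|---|
| Hochberg over all seven t-tests | 0.04-0.05 | (reference) |
| MANOVA gate, post hoc unadjusted, one survey | 0.19-0.21 | 28-36% |
| Same, two or three surveys | 0.13-0.16 | 19-23% |
| MANOVA gate, Hochberg inside the survey, one survey | about 0.04 | 3-14% |
| Same, two or three surveys | 0.06-0.11 | 9-13% |

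**4. The combined reading.** Suppose a MANOVA gate is followed by Hochberg over all tests. With no true change, the chance of any false positive is 0.013-0.044. With the one true change, power for it is 0.70-0.845, against 0.842-0.845 without the gate. The loss is largest with one survey of seven scores and correlation 0.3.

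**5. Number of tests and power.** The formula in step 2 with d = 0.914 (noncentrality 0.914 x 4.472 = 4.088) gives:

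| Tests | 0.05/m | Critical t | Power |
|---|---|---|---|
| 7 | 0.00714 | 3.014 | 0.842 |
| 8 | 0.00625 | 3.074 | 0.828 |
| 9 | 0.00556 | 3.127 | 0.815 |
| 10 | 0.00500 | 3.174 | 0.803 |

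At the high end (d = 1.248) power falls only from 0.990 to 0.985 over the same range.

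**The case against.** **The two passages can be combined.** The post hoc tests could be the paired tests, with all their p-values adjusted together by Hochberg. Step 4 shows that this reading does not inflate error. However, no section states it, and the statistical sections assign all data to paired t-tests or Friedman's test, which leaves MANOVA no role. If it was intended, it costs power that the power statement does not allow for.

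**The comparison rests on assumptions.** This stands. Instrumentation names one instrument, PROMIS, and gives no number of surveys, so the figures illustrate the conflict and do not predict this trial's error rate. The conflict between the passages does not depend on them.

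**A reader might infer that only the Hochberg rule keeps error at .05.** The figures do not support that. With no true change, Hochberg inside each of two surveys gives 0.042-0.053, and the combined reading stays below .05. With Friedman's test (two-period chi-square) and one true change, Hochberg over all seven gives about 0.048-0.054, so it is not strictly below .05 either.

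**A reader might also infer that the plan never defines its tests.** The Hypothesis expects that families "will experience increases in health-related quality of life, mental health, and physical activity", whereas PROMIS "will be used to examine mental health and physical activity", and the visible text has no count. But the PROMIS forms are attached to the plan and are not shown here. They may name the scales, subscales and respondents. What can be said is narrower: the visible text does not tie 0.007 to a number of tests. The forms would not settle which of the two analysis rules applies.

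**Conclusion.** The point holds as a contradiction in current text: a MANOVA for each survey with unnamed post hoc tests, against paired tests with one Hochberg adjustment. It should be corrected. Under the stated assumptions, with one true change, the two rules give different lists of significant scales in about 19-36% of trials if post hoc tests are unadjusted, and in about 3-14% if Hochberg is applied inside each survey. The excess of false positives ranges from none (one survey, Hochberg inside it) to about 0.21 against 0.05 (one survey, unadjusted). The documents do not say where in that range the trial would fall.

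Alpha 0.007 is not shown to be wrong. It agrees with one Hochberg family of seven tests, and so with the statistical sections. If seven already counts every scale and subscale test, no power is lost. If there are eight to ten, the low end falls by 1 to 4 points.

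**What to change.** 1. Under Instrumentation, delete the MANOVA sentence or label that analysis descriptive. Keep the paired t-test or Friedman's test, with one Hochberg adjustment over all scale and subscale tests.
2. In the power statement, give the number of tests behind 0.007. If it is seven, the alpha stands. If the scale and subscale tests are not seven, either restate alpha as 0.05 divided by the actual number and the power with it (the low end of 0.84 becomes about 0.83, 0.82 or 0.80 for 8, 9 or 10 tests), or label the extra scores exploratory.

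The cost is a change of wording, with no new data and no change in N. Dropping the MANOVA takes nothing from the stated power, which refers to tests at alpha 0.007 and to no MANOVA.

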## Statistical Analyses

All data will be analyzed by paired t-tests/Friedman's test. To accommodate multiple comparisons, all p-values will be adjusted using Hochberg's adjustment.

## Statistical Analysis Overview

The evaluation team will collect questionnaires pre and post implementation. Each facilitator will have an envelope to return to the evaluation team. The evaluation team will enter the data into SAS database and analyze the results. We will evaluate differences between pre and post measures using a paired t-test for normally distributed data and Friedman's test for non-normally distributed scales.

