## Comparison Group Selection

Each subject will serve as their own control.

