### **Other Method Name**

Friedman's test

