### **Estimation Parameter**

Mean Difference (Final Values)

Median Difference (Final Values)

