### **Parameter Dispersion Type**

Standard Error of the Mean

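### With only pre and post scores, Friedman's test is the sign test: it ignores the size of each change, and the stated power of 0.84 to 0.99 should not be read as covering it

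*Combined protocol and SAP*

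**What the plan says.** Instrumentation, and again the Statistical Analysis Overview, fix two measurement occasions: "The evaluation team will collect questionnaires pre and post implementation". Comparison Group Selection makes the comparison within subject: "Each subject will serve as their own control".

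The Statistical Analysis Overview chooses the test by distribution: "We will evaluate differences between pre and post measures using a paired t-test for normally distributed data and Friedman's test for non-normally distributed scales". Statistical Analyses and Statistical Test of Hypothesis repeat the pair of tests ("All data will be analyzed by paired t-tests/Friedman's test"), and Other Method Name lists "Friedman's test".

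The Comments section on sample size takes a 5% increase, a standard deviation of 0.1 and alpha 0.007, and reports that "power at N = 20 ranges from a low of 0.84 to a high of 0.99 calculated using SAS proc power". It does not name the test. Estimation Parameter lists a mean difference and a median difference. The only dispersion measure listed is "Standard Error of the Mean".

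**The concern.** Friedman's test is built for three or more related measurements. With two, it ranks each pair 1 and 2, so a small improvement and a large one count the same. The usual rank test for paired data, the Wilcoxon signed-rank test, keeps the size of the change.

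In a 20-family pilot, a subscale sent to this branch will generally have less chance of showing a real change than it would under a signed-rank test. A reader may also take 0.84 to 0.99 as its power. An increase and a standard deviation describe a test on means. They do not determine sign-test power, which depends on the probability that a subject improves and on how many subjects show no change.

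Two smaller points belong here. The plan attaches non-normality to the scales, whereas the paired t-test needs approximately normal paired differences; a subscale could go to the weaker test only because its raw scores are skewed. A standard error of the mean also does not describe the precision of a median difference.

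**Working it through.** **Inputs.** From the plan: two occasions, N = 20, alpha 0.007, a 5% increase, SD 0.1, stated power 0.84 to 0.99, two-sided t-test, Hochberg adjustment, overall level 0.05. Assumed: 5% means 0.05 on the scale of the SD; the stated power is for the paired t-test; seven tests, since 0.05/7 = 0.007; no unchanged scores.

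**1. The plan's own figure.** Taking 0.1 as the SD of change, the standardized change is d = 0.05/0.1 = 0.5. The noncentral t with 19 df and noncentrality 0.5 × √20 = 2.24 gives two-sided power 0.25 at alpha 0.007. The stated range is not reproduced. If 0.1 is the SD of the scores, the SD of change is 0.1 × √(2(1 − ρ)), and the range needs an unstated pre-post correlation ρ of about 0.85 to 0.92. Solving backwards, the t-test reaches 0.84 at d = 0.914 and 0.99 at d = 1.248. These two effects are used below so that the comparison starts from the plan's stated power.

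**2. Friedman with two occasions.** Let n+ subjects rise and n− fall, with n = n+ + n−. The rank sums are n + n+ and n + n−. For k = 2 the statistic is

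(2/n)[(n + n+)² + (n + n−)²] − 9n = (n+ − n−)²/n,

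which is the large-sample sign-test statistic. Simulated sets of 20 pairs agree: 15 increases give 5.0, and 14 give 3.2.

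**3. Rejection rule at n = 20.**

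| Changes one way | Chi-square p | Exact two-sided p |
|---|---|---|
| 15 | 0.0253 | 0.0414 |
| 16 | (16 − 4)²/20 = 7.2, p = 0.0073 | 0.0118 |
| 17 | 0.0017 | 0.0026 |

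At alpha 0.007, 17 of 20 are needed, with an actual size of 0.0026.

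**4. Power at alpha 0.007, normal differences.** Sign-test power is P(Bin(20, Φ(d)) ≥ 17) plus the opposite tail.

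| d | Φ(d) | Paired t | Signed-rank | Sign/Friedman |
|---|---|---|---|---|
| 0.5 | 0.69 | 0.25 | 0.23 | 0.09 |
| 0.914 | 0.82 | 0.84 | 0.81 | 0.50 |
| 1.248 | 0.89 | 0.99 | 0.99 | 0.84 |

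**5. Non-normal differences**, alpha 0.007, d = 0.914, 100,000 simulations per shape, exact signed-rank critical values:

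| Shape | Sign | Signed-rank |
|---|---|---|
| Uniform | 0.27 | 0.75 |
| t, 5 df | 0.67 | 0.86 |
| Laplace | 0.71 | 0.85 |
| Exponential, left skew | 0.66 | 0.77 |
| Exponential, right skew | 0.92 | 1.00 |
| Gamma(4), left skew | 0.57 | 0.78 |
| Gamma(4), right skew | 0.53 | 0.91 |

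At alpha 0.05 and the same effect the signed-rank test was again higher in every shape, sometimes barely (left exponential 0.945 against 0.937).

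**6. Later Hochberg steps** (seven tests, normal, d = 0.914):

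| Level | Friedman, chi-square p | Paired t |
|---|---|---|
| 0.0071 | 0.50 | 0.84 |
| 0.0083 to 0.025 | 0.71 | 0.86 to 0.94 |
| 0.05 | 0.86 | 0.97 |

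At 0.0083 and 0.01 the 0.71 relies on the chi-square p for 16 of 20. The exact test still needs 17 there and has power 0.50.

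**The case against.** **It is a preference, not an error.** The exact sign test is valid, and Friedman's test suits a within-subject design. This stands, and is why the point is a recommended improvement.

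**The normal-case figures describe data that would go to the t-test.** Fair. The comparison for this branch is step 5, where the signed-rank test was ahead in every shape, by 0.08 to 0.48.

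**The sign test does not always lose.** True. For left-skewed exponential differences and d = 0.5, it was ahead at alpha 0.05 (0.72 against 0.69) and at 0.0125 (0.53 against 0.48). At d = 0.914 and 0.0125 the two were level at 0.84. With the chi-square p at 0.0083 it led in two cases, left exponential at 0.914 (0.84 against 0.80) and Laplace at 0.5 (0.42 against 0.38), but that rule has an actual size of 0.0118. These are exceptions.

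**The replacement gives up robustness.** This is the strongest objection. With a true median change of zero, the signed-rank test rejected 10% to 11% at nominal 0.05 and 1.6% to 1.8% at 0.007 under exponential and lognormal skew; the sign test stayed at 4% and 0.3%. Under milder skew (gamma, shape 4) the signed-rank figures were 6.0% and 0.8%. If the listed median difference means the median paired change, the sign test addresses it directly, whereas the signed-rank test does so only when differences are symmetric. A sign-test sensitivity check is therefore needed.

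**Instrumentation also specifies MANOVA.** That is a separate conflict, and it does not remove the Friedman branch.

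**Conclusion.** The concern holds. That Friedman's test here is the sign test is algebra and depends on no assumption about the data. The loss depends on shape and level: at alpha 0.007 and a standardized change of 0.914, power is 0.50 against 0.81 for the signed-rank test under normality, and 0.27 to 0.92 against 0.75 to 1.00 over the non-normal shapes tried. The gap narrows at the less strict Hochberg levels.

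These sizes rest on reading the stated power as that of a paired t-test, on effects solved back from that power, on seven tests, and on no tied pairs. Unchanged scores carry no direction and reduce the effective sample. If the plan's printed inputs are read directly, every test is weak (0.25, 0.23 and 0.09), and changing the test would not rescue the pilot. The normality wording and the dispersion listing are secondary.

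**What to change.** - **Test.** In Statistical Analyses, Statistical Analysis Overview, Statistical Test of Hypothesis and Other Method Name, replace Friedman's test. Suggested wording: *Pre-post change will be tested with the paired t-test if the paired differences are approximately normal, otherwise with the Wilcoxon signed-rank test on the paired differences; if these are strongly skewed, an exact sign test is reported as a sensitivity check.* State beforehand how normality and skewness of the differences will be judged. Using the paired t-test throughout, with the signed-rank test as sensitivity analysis, would avoid choosing the test from the same 20 observations.
- **Power.** In the Comments section on sample size, name the test the range refers to. If Friedman's test is kept, call it a sign test, use the exact p-value, and give its own power with the assumed probability of improvement and tie rate.
- **Estimates.** In Estimation Parameter and Parameter Dispersion Type, report the Hodges-Lehmann estimate of paired change with its 95% CI beside the signed-rank result, and keep the standard error or t-based interval for the mean change.

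The cost is SAP wording and a SAS procedure run on the differences (PROC UNIVARIATE); no new data are needed. The drawback is the signed-rank test's inflated Type I error under strong skew, which the sign-test check would help to expose.
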